## **Funder**

Dexcom

This protocol describes the study and provides information about procedures for entering participants. Every care was taken in its drafting, but corrections or amendments may be necessary. These will be circulated to investigators in the study. Problems relating to this study should be referred, in the first instance, to the Chief Investigator.

This study will adhere to the principles outlined in the NHS Research Governance Framework for Health and Social Care (2nd edition). It will be conducted in compliance with the protocol, the Data Protection Act and other regulatory requirements as appropriate.

## STUDY SUMMARY

**TITLE** Impact on Hypoglycaemia Awareness of Real Time CGM and Intermittent Continuous Glucose Data

**DESIGN** Randomised open-label parallel group study

**AIMS** This study aims to assess the impact of real-time continuous glucose monitoring and intermittently viewed continuous glucose data on frequency, duration and severity of hypoglycaemia in people with type 1 diabetes and impaired awareness of hypoglycaemia.

[figure not shown]
**OUTCOME MEASURES** The primary outcome is percentage of time spent in hypoglycaemia (<3.3mmol/L, 60mg/dL) measured by a continuous glucose sensor. Secondary outcomes include other measures of hypoglycaemia, overall glucose status and patient reported quality of life.

**POPULATION** Adults with type 1 diabetes and impaired hypoglycaemia awareness

**ELIGIBILITY** Participants identified in type 1 diabetes clinics and by recruitment from existing databases.

**DURATION** 18 weeks

## REFERENCE DIAGRAM

# 1. INTRODUCTION

## 1.1 BACKGROUND

Type 1 diabetes (T1DM) is characterised by autoimmune destruction of the pancreatic beta cell, leading to absolute deficiency of insulin. Management of T1DM requires exogenous insulin administration, aiming for glucose concentrations as close to physiological values as possible. Intensive management of T1DM improves glucose control and reduces the risk of microvascular diabetes complications and cardiovascular disease. However, optimal control remains challenging to achieve and intensive insulin treatment increases the risk of severe hypoglycaemia, with lower glucose values also associated with an increased frequency and severity of moderate hypoglycaemia.

Hypoglycaemia is associated with morbidity and even mortality, and places a financial burden on health systems. Severe hypoglycaemia costs £13million per year in direct NHS costs and significantly more in indirect costs to people with diabetes, their families, friends and employers. Hypoglycaemia is one of the most common metabolic complications of the treatment of type 1 diabetes. Mild hypoglycaemia results in a variety of symptoms, including tremor, hunger, and anxiety, and, as glucose concentrations fall lower patients may develop cognitive impairment. Severe hypoglycaemia, defined as hypoglycaemia requiring the assistance of another person to treat, may cause seizures, coma, or death. Between 4 and 10% of deaths in people with type 1 diabetes are attributed to hypoglycaemia and the risk of severe hypoglycaemia increases 6-fold in people with impaired awareness of hypoglycaemia. Avoidance of hypoglycaemia is associated with restoration of hypoglycaemia awareness and this may be enabled by the use of diabetes technology.

Type 1 diabetes directly affects 300,000 people in the United Kingdom. In the UK diabetes consumes more than 10% of the National Health Service budget and in the USA a relatively greater amount is spent on type 1 compared with type 2 diabetes (8.6% of the diabetes budget compared with 5.6% of diabetes prevalence).

Diabetes technologies, such as continuous glucose monitoring and insulin pump therapy can improve overall glucose control and may reduce the frequency and severity of hypoglycaemia when used in combination with education and support for self-management. However, despite this, 72.4% of people with T1DM in England have an HbA1c over 58mmol/mol (7.5%) and 16.6% have an HbA1c over 86mmol/mol (10%). Women aged 15 to 34 have a ninefold increase in mortality risk compared with women of the same age without diabetes. Diabetes remains the leading cause of blindness, amputation and end-stage renal failure in the developed world.

In type 1 diabetes real-time continuous glucose monitoring (CGM) improves overall glucose control in all age groups when used continuously, reduces hypoglycaemia in people with an HbA1c <7.0%, and may reduce severe hypoglycaemia.

The Dexcom G4 and G5 systems are CE marked real-time continuous glucose sensor systems which provide dynamic glucose information to people with type 1 diabetes, or their carers. These glucose data are updated every 5 minutes. Sensors are used for 7 days before replacement. The G4 system sensor requires calibration to capillary blood glucose values twice a day and verification with a capillary blood glucose test before treating diabetes based on sensor reported data. The Dexcom G5 can be used non-adjunctively (does not require pre-treatment verification with capillary blood glucose before diabetes treatment decisions). The G5 system does require twice a day calibration with capillary blood glucose.

The Libre intermittent glucose monitoring system provides up to 8 hours of retrospective continuous glucose monitoring data to users when the monitor is waved in proximity with the sensor. In contrast to real-time CGM the Libre system sensor is used for 14 days and is non-adjunctive.

## 1.2 RATIONALE FOR CURRENT STUDY

This clinical study proposes to assess the impact of Libre on frequency, duration and severity of hypoglycaemia, compared with non-adjunctive use of the Dexcom G5 real-time CGM and will focus on people with impaired awareness of hypoglycaemia.

Hypothesis: Libre intermittent CGM has an equivalent impact on hypoglycaemia to real-time CGM.

## 2. STUDY OBJECTIVES

**Primary outcome:** % time spent in hypoglycaemia (<3.3mmol/L, 60mg/dL)

**Secondary outcome:** % time spent in hypoglycaemia (<2.8mmol/L, 50mg/dL)  
% time spent in hypoglycaemia (<3.9mmol/L, 70mg/dL)  
% time in euglycaemia (3.9-7.8mmol/L, 70-140mg/dL)  
% time spent in target (3.9-10mmol/L, 70-180mg/dL)  
% time spent in hyperglycaemia (>10mmol/L, 180mg/dL)  
Number hypoglycaemic excursions  
Severe hypoglycaemia (requiring third party assistance to treat)  
MAD%  
Glucose variability  
HbA1c  
Sensor usage (compliance)  
Sensor life and % of sensor failure  
% of reported sensor readings compared to total possible readings  
Change in insulin dosage  
Diabetes treatment satisfaction  
CGM usability  
Diabetes quality of life  
Fear of hypoglycaemia  
Healthcare professional qualitative feedback

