### **Randomisation**

Participants will then receive standardised CGM education for the Dexcom and Abbott devices from study staff and will be randomised to Libre or the Dexcom G5 system with receiver. All education will be delivered by the research nurse from a predefined curriculum and will be supported by independent written materials. Both the Libre and G5 systems will be used non-adjunctively (without capillary blood glucose verification before making a treatment decision, in accordance with product licences) but participants will be instructed to test their capillary blood glucose if symptoms of hypo- or hyperglycaemia occur, in case of sensor failure or if the sensor glucose is out of the desired range. Participants will use the G5 sensor with the accompanying receiver and will change sensor every seven days (or sooner in the event of sensor failure). Real-time glucose data will be available to participants. Participants will use the Libre sensor with the accompanying receiver and will change the sensor after 14 days (or sooner in the event of sensor failure). Participants will be enabled to use the Libre monitor to assess glucose value and trend as often as they choose.

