## **7. STATISTICS AND DATA ANALYSIS**

With 40 participants, we can demonstrate as significant at 80% power a mean difference in time in hypoglycaemia between Libre and G5 of 0.45 standard deviations. Any smaller difference will be distinguished as signifying no significant difference between Libre and CGM. To allow for a 10-15% drop out, 45 participants will be recruited. Randomisation will be stratified by HbA1c quartiles (5-6%, 6.1-7.0%, 7.1-8.0% and 8.1-9%). Randomisation will be done using sealedenvelope.com.

Baseline data will be taken from the first 14 days of monitoring and outcomes will be calculated from the last 30 days in each treatment period.

Analysis will be by intention to treat. The primary outcome will be assessed by two-tailed unpaired t-test. For secondary outcomes parametric data will be compared between the two study arms by two-tailed unpaired t-test for continuous variables. Non-parametric data will be compared using a Kruskal Wallis test.

Data and all appropriate documentation will be stored for a minimum of 10 years after the completion of the study, including the follow-up period.

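### The number of hypoglycaemic excursions has no recorded-time denominator, so a literal count would favour whichever arm records less sensor data

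*Combined protocol and SAP*

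**What the plan says.** The Study Summary states the aim as the effect of the two systems on "frequency, duration and severity of hypoglycaemia". Among the secondary outcomes in section 2 is "Number hypoglycaemic excursions", with no threshold, minimum duration, time unit or denominator. The glucose-range outcomes in the same list are all percentages of time. The list also includes sensor usage and, as an outcome in its own right, the percentage "of reported sensor readings compared to total possible readings".

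Section 7 takes baseline from the first 14 days of monitoring and states that "outcomes will be calculated from the last 30 days in each treatment period". Secondary outcomes are compared between arms by unpaired t-test or Kruskal-Wallis test. No rate, offset or minimum-wear rule is given.

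The two devices acquire data differently. Section 1.1 says of the Dexcom systems that "These glucose data are updated every 5 minutes", and that Libre "provides up to 8 hours of retrospective continuous glucose monitoring data to users when the monitor is waved in proximity with the sensor". Under Randomisation in section 6: "Participants will be enabled to use the Libre monitor to assess glucose value and trend as often as they choose". Sensors are changed every 7 days for G5 and every 14 days for Libre.

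**The concern.** A percentage of time carries its own denominator. If gaps in the record are unrelated to glucose, the percentage stays unbiased however much is missing. A count does not have this property: losing recorded time loses excursions even when the loss is entirely random. This is therefore a different problem from selective data loss in the percentage outcomes, and protecting those outcomes does not protect this one.

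The plan itself expects recorded time to vary, since it makes capture an outcome. For Libre, intervals of more than 8 hours between scans can lose data, and scanning is left to the participant. For G5, data can be lost through more frequent sensor changes and the twice-daily calibration requirement. If these losses do not balance, a lower count in one arm may reflect missing data and yet be read as fewer episodes. Frequency is the first element of the stated aim, and this is its only sensor-based measure.

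**Working it through.** The plan states no expected excursion count, excursion rate or capture fraction, so it has no figure of its own to reproduce here. Its one power statement concerns the primary outcome and is not used.

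**Inputs from the documents.** Outcome window 30 days and baseline window 14 days (section 7). Two parallel arms with 40 participants (section 3), taken as 20 per arm. Unpaired t-test (section 7).

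**Inputs assumed.** True rate of 1 excursion per day in both arms; captured fraction 95% in one arm and 90%, 85%, 75% or 60% in the other; between-person coefficient of variation (CV) of the true rate 0.3, 0.6 or 1.0; two-sided 5% test.

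**Step 1: expected count.** When gaps are long relative to an excursion and unrelated to glucose,

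expected count = rate × 30 × capture.

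At equal true rates, the ratio of counts is therefore the ratio of captures.

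| Capture | Expected count | Ratio to the 95% arm |
|---|---|---|
| 95% | 1 × 30 × 0.95 = 28.5 | 1.00 |
| 90% | 27.0 | 0.90/0.95 = 0.95 |
| 85% | 25.5 | 0.85/0.95 = 0.89 |
| 75% | 22.5 | 0.75/0.95 = 0.79 |
| 60% | 18.0 | 0.60/0.95 = 0.63 |

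Divided by recorded days, every row gives 1.0 per day: for example 28.5/(30 × 0.95) and 22.5/(30 × 0.75).

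**Step 2: false-positive rate.** Gamma-Poisson counts were simulated with 20 per arm and equal true rates, 20,000 trials per setting. The t-test was applied to raw counts and to counts per recorded day.

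| Capture | Raw, CV 1.0 | Raw, CV 0.6 | Raw, CV 0.3 |
|---|---|---|---|
| 95% v 90% | 4.9% | 5.6% | 7.9% |
| 95% v 85% | 5.7% | 8.1% | 16.1% |
| 95% v 75% | 9.7% | 20.6% | 52.0% |
| 95% v 60% | 25.4% | 58.4% | 97.1% |

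Per recorded day, the rate was 4.5% to 5.1% throughout. At 0.5 excursions per day, the raw-count range from CV 1.0 to CV 0.3 is 5.7% to 12.9% for 95% v 85%, and 9.4% to 42.0% for 95% v 75%.

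**Step 3: how far proportionality holds.** Short gaps can leave part of an excursion visible, or split it in two. In an illustrative simulation with 45-minute excursions and a 15-minute minimum (both assumed), 75% capture kept about 87% of the count with 30-minute gaps, and about 76% to 77% with gaps of 4 to 8 hours. Step 1 therefore describes long gaps, such as a missed scan or a late sensor replacement; short gaps do less harm.

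**Step 4: comparison with baseline.** At an unchanged rate and full capture, the follow-up count exceeds the baseline count by 30/14 = 2.1 times. This needs no assumption about capture. The plan specifies no change-from-baseline test, so the harm here is to any descriptive comparison.

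**The case against.** The strongest reply is that the plan is silent on normalisation and does not reject it. A reader might infer that the trial has committed to an undivided count. The documents do not say so: section 2 gives a label, section 7 gives a window, and an analyst could reasonably report a rate. That stands, and the defect is an unstated denominator. But nothing in the plan rules out the literal count either, and the word used is a number where the neighbouring range outcomes are percentages.

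A reader might also infer that this is the plan's only measure of hypoglycaemia frequency. It is not. Severe hypoglycaemia, defined by the need for third-party help, is listed next and does not depend on sensor capture.

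Nor do the documents show that the comparison will be biased, or in whose favour. They give no capture figures, both devices have plausible routes to data loss, and these could cancel. At 95% against 90% the inflation is negligible unless between-person variation is small, and the larger figures depend strongly on the assumed CV.

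Capture is itself an outcome, so an imbalance would be reported and an alert reader could see it. That helps interpretation but does not correct the test. Finally, the primary outcome is a percentage of time and is untouched by this point.

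**Conclusion.** The point holds as a missing denominator on a secondary outcome that matters to the stated aim. Read literally, the count falls as recorded time falls, so unequal capture would produce an apparent difference at equal true rates. Under the assumptions listed, the size is a count ratio of about 0.89 with a 6% to 16% false-positive rate at 95% against 85% capture, and about 0.79 with 10% to 52% at 95% against 75%. Direction and actual size cannot be determined from the documents, and with equal capture there is no between-arm bias. The incompatibility with the 14-day baseline holds regardless.

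It would go too far to say that the absence of a per-excursion duration outcome is an error. Percentage of time below three thresholds already reflects cumulative duration.

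**What to change.** In section 2, replace the item with: hypoglycaemic excursions per 24 hours of recorded sensor data. State one glucose threshold, one minimum duration and one rule for when an excursion ends, and apply them to both devices' readings on a common time grid, using the coarser of the two recording intervals. Say how an excursion interrupted by a gap is counted, and state a minimum amount of recorded data for a participant to contribute.

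In section 7, analyse either participant-level rates with the planned tests, or a count model that allows for overdispersion, with log recorded hours as offset. Report recorded hours by arm beside the result, and express baseline in the same unit. Mean duration per excursion may be added if wanted.

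The cost is a line in section 2, a few lines in section 7 and some derivation code. The reading-capture outcome already requires the recorded time to be extracted, so no new data are needed.

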## 3. STUDY DESIGN

Randomised parallel group trial over 18 weeks in 40 adult participants with type 1 diabetes and impaired hypoglycaemia awareness

## 4. PARTICIPANT ENTRY

### 4.1 PRE-REGISTRATION EVALUATIONS

HbA1c  
Serum C-peptide  
Plasma glucose  
Gold score

I HART CGM  
Protocol v2.0  
30th August 2015

#### 4.2 INCLUSION CRITERIA

Adults over 18 years of age

Type 1 diabetes confirmed on the basis of clinical features and a fasting c-peptide <200 pmol/L

Severe hypoglycaemic event in the last 12 months requiring third party assistance OR a Gold Score  $\geq 4$

Type 1 diabetes for greater than 3 years

On an intensified multiple dose insulin injection regimen for > 6 months (MDI)

Previous type 1 diabetes structured education (either group or 1:1)

#### 4.3 EXCLUSION CRITERIA

Use of CGM or Libre device within the last 6 months (except short periods of diagnostic blinded use under clinic supervision)

Use of regular paracetamol

Pregnant or planning pregnancy

Breastfeeding

Enrolled in other clinical trials, except at the discretion of the chief investigator

Have active malignancy or under investigation for malignancy

Severe visual impairment

Reduced manual dexterity

Unable to participate due to other factors, as assessed by the Chief Investigators

#### 4.4 WITHDRAWAL CRITERIA

Participants will be withdrawn if their ability to give informed consent is impaired. Participants will also be withdrawn, at the chief investigators discretion, if glucose control is negatively impacted by the use of either intervention.

## 5. ADVERSE EVENTS

#### 5.1 DEFINITIONS

**Adverse Event (AE):** any untoward medical occurrence in a patient or clinical study subject.

**Serious Adverse Event (SAE):** any untoward and unexpected medical occurrence or effect that:

- **Results in death**
- **Is life-threatening** – *refers to an event in which the subject was at risk of death at the time of the event; it does not refer to an event which hypothetically might have caused death if it were more severe*
- **Requires hospitalisation, or prolongation of existing inpatients' hospitalisation**
- **Results in persistent or significant disability or incapacity**
- **Is a congenital anomaly or birth defect**

Medical judgement should be exercised in deciding whether an AE is serious in other situations. Important AEs that are not immediately life-threatening or do not result in death or hospitalisation but may jeopardise the subject or may require intervention to prevent one of the other outcomes listed in the definition above, should also be considered serious.

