### 5.3.1 Non serious AEs

All such events, whether expected or not, should be recorded.

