### 5.3.2 Serious AEs

An SAE form should be completed and faxed to the Chief Investigator within 24 hours. However, hospitalisations for elective treatment of a pre-existing condition do not need reporting as SAEs.

All SAEs should be reported to the NRES Committee London - Hampstead where in the opinion of the Chief Investigator, the event was:

- 'related', ie resulted from the administration of any of the research procedures; and
- 'unexpected', ie an event that is not listed in the protocol as an expected occurrence

Reports of related and unexpected SAEs should be submitted within 15 days of the Chief Investigator becoming aware of the event, using the NRES SAE form for non-IMP studies. The Chief Investigator must also notify the Sponsor of all SAEs.

Local investigators should report any SAEs as required by their Local Research Ethics Committee, Sponsor and/or Research & Development Office.

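### Section 5.1 makes being unexpected part of the SAE definition, so an expected hospitalisation for severe hypoglycaemia can, read literally, escape the 24-hour form and sponsor notification

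*Combined protocol and SAP*

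**What the plan says.** Section 5.1 gives two definitions. An adverse event is "any untoward medical occurrence in a patient or clinical study subject", with no condition on expectedness. An SAE is "any untoward and unexpected medical occurrence or effect that" satisfies at least one of five criteria: death, threat to life, hospitalisation, lasting disability, or congenital anomaly. A closing paragraph adds that "Medical judgement should be exercised in deciding whether an AE is serious in other situations".

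Section 5.3.2 sets the duties that follow from SAE status. For every SAE, "An SAE form should be completed and faxed to the Chief Investigator within 24 hours", and the Chief Investigator must inform the sponsor. Local investigators' duties to their own committee, the sponsor or the research office are also tied to SAEs. Reporting to the ethics committee is narrower: the SAE must be related and also unexpected, the latter meaning "an event that is not listed in the protocol as an expected occurrence". Admissions for elective treatment of a pre-existing condition are exempted.

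For non-serious events, section 5.3.1 says only: "All such events, whether expected or not, should be recorded". The opening of section 5.3 asks for all adverse events to be reported, without a deadline or a named recipient.

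**The concern.** Expectedness appears twice: once inside the SAE definition, and again as the test for which SAEs go to the ethics committee. In the first position it does more than the protocol seems to intend. An investigator who regards an admission as expected can conclude from section 5.1 that it is not an SAE, and then neither the 24-hour form nor the sponsor notice is triggered.

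This matters here because severe hypoglycaemia is an event that an investigator could reasonably call expected in this population. Both devices are used without a routine capillary check before treatment decisions (section 6, Randomisation), so such an admission may bear on how a device performs. Section 4.4 leaves withdrawal for worsened glucose control to the Chief Investigator's discretion, which depends on timely information.

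**Working it through.** The plan has no figure to reproduce. The check follows one event, a hospitalisation for severe hypoglycaemia, through section 5.

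**Step 1: is the event foreseeable from the protocol?** Yes, on three grounds.
- Section 1.1 says severe hypoglycaemia may lead to seizures, coma or death, and that its risk is 6-fold higher with impaired awareness.
- Section 4.2 makes a severe event in the previous 12 months one of two alternative entry routes. The other is a Gold score of 4 or more.
- Section 2 lists severe hypoglycaemia as a secondary outcome.

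**Step 2: does it meet a seriousness criterion?** Yes: "Requires hospitalisation, or prolongation of existing inpatients' hospitalisation".

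**Step 3: what must be done?** That depends on how *unexpected* in section 5.1 is read.

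| Reading of section 5.1 | SAE? | 24-hour form | Sponsor notice | Ethics committee |
|---|---|---|---|---|
| Ordinary sense; event judged expected | No | Not required | Not required | Not required |
| Section 5.3.2 sense; event not on a list | Yes | Required | Required | If related |
| Condition deleted; event expected | Yes | Required | Required | Not required |
| Condition deleted; event unexpected | Yes | Required | Required | If related |

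The first two rows are both open to an investigator under the current text, and they give different duties for the same admission. In the last two rows the form and the sponsor notice no longer depend on expectedness, which then decides only the ethics committee report.

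**Step 4: what happens to the event in the first row?** It is still an adverse event. It falls either under section 5.3.1, whose title does not fit an admission to hospital, or under the general instruction in section 5.3 alone. Neither sets a deadline or requires notice to the sponsor.

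**Step 5: does the medical-judgement clause close the gap?** Only in part. It is discretionary and is directed mainly at important events that fall short of death or hospitalisation. An admission that already meets a listed criterion but is judged expected is not the case it describes.

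**Step 6: does any analysis depend on SAE status?** No. Section 7 compares the arms on the primary and secondary outcomes. Section 2 lists no SAE endpoint, and it defines severe hypoglycaemia by the need for third-party help, not by SAE status.

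**Step 7: scale.** With 45 recruits and 18 weeks each, follow-up is at most 45 × 18 = 810 participant-weeks, or 810 / 52 ≈ 15.6 participant-years, assuming nobody drops out. The 18 weeks are 2 of run-in, 8 randomised and 8 of follow-on, in which all are offered the G5. No rate of hospitalised severe hypoglycaemia is given, so no expected count can be calculated.

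**The case against.** The strongest reply is that the only meaning the protocol gives to *unexpected* is the one in section 5.3.2, which refers to a list of expected occurrences. No such list appears in the available text. Being mentioned in the background, the entry criteria or the outcomes is not the same as being listed as expected. On that meaning, a hospitalisation for severe hypoglycaemia is unexpected, is an SAE, and carries both duties. The rest of section 5.3.2 points the same way: it selects unexpected events from among SAEs, which presupposes that some are expected, and it exempts elective admissions, which would hardly be needed if foreseeable events were already outside the definition.

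Much of this stands as evidence of intent: the wording in section 5.1 looks like a drafting slip. It does not remove the problem. The list-based meaning is given for ethics committee reporting, and section 5.1 does not refer to it. An investigator who reads section 5.1 as written reaches the opposite answer. The reply is also fragile: adding a list of expected events to make the section 5.3.2 test workable would, on that same meaning, take every listed event out of SAE status.

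The reply is right about the consequences. A reader might infer that such admissions would go unrecorded. The documents do not support that, because sections 5.3 and 5.3.1 still call for reporting or recording, and severe hypoglycaemia is collected as an outcome. A reader might also infer that uneven classification would bias a comparison of SAEs between the devices in an open-label trial. The plan specifies no such comparison.

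**Conclusion.** The inconsistency is real and should be corrected. Sections 5.1 and 5.3.2 use *unexpected* in two roles that do not fit together. On a literal reading, an expected event that meets a seriousness criterion loses the 24-hour form and the sponsor notice. On the other available reading it keeps both, so classification could vary between investigators.

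The size is limited. What is at risk is the promptness of notice to the Chief Investigator and the assurance that the sponsor is told, not the existence of the record or any planned efficacy result. The number of events affected cannot be estimated from the documents and may be small in a trial of this size. It would go too far to say that participants are enrolled because they have had severe hypoglycaemia, since a Gold score of 4 or more is enough for entry on that criterion.

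The conclusion assumes that an investigator could reasonably judge severe hypoglycaemia expected, which the protocol's own description supports. It also takes the public text as it stands, without a list of expected occurrences. If one exists elsewhere, the events on it would be outside the SAE definition on either reading.

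**What to change.** In section 5.1, delete the words that add expectedness to the SAE definition, so that seriousness rests only on the listed criteria and the medical-judgement clause. Leave *related* and *unexpected* in section 5.3.2 as the test for ethics committee reporting, and use them nowhere else. If a list of expected occurrences is later added to support that test, make the deletion first.

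The cost is two words and possibly a few more SAE forms. No outcome, sample size or analysis changes.
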